6.7. Changes to Protocol-Specified Analyses of Semen and Hormone Data

The protocol specified an analysis of covariance (ANCOVA) model adjusting for baseline value and stratification factors to estimate treatment differences (95% CI) for the continuous endpoints at timepoints where analysis was to be conducted for continuous semen parameter and hormone data. Quantile regression was used in place of an ANCOVA model as medians were thought to be a more appropriate estimate than means for this data which is potentially skewed with outliers.

Disease type was not included as a stratification factor for the stratified Mantel-Haenszel test for the primary endpoint or as a dependent variable in quantile regression models for sperm/semen parameters (secondary endpoints) or hormones (exploratory endpoints) since only a few RA subjects were enrolled. The lowest 2 levels (15 - 25 M/mL and > 25 - 50 M/mL) for sperm concentration strata were combined in these analyses due to the small number of subjects in the lowest sperm concentration stratum.

7. ASSESSMENT OF RESPONDER/NON-RESPONDER AND DISEASE WORSENING

Physician Global Assessment of Disease Activity (PhGADA) was used to determine whether a subject was an “Arthritis Responder” (defined as an improvement in PhGADA of at least 20% compared to baseline at the specified assessment time point) or “Arthritis Non-responder” (defined as a subject who does not fulfill the definition of responder at the specified assessment timepoint). The physician (who had access to disease assessments described in Protocol Sections 6.18 through 6.23 [as appropriate]) drew a perpendicular line on a 100-millimeter (mm) visual analogue scale (VAS) representing the subject’s disease severity and measured the distance (in mm) between the “no disease activity” anchor (at 0) and the mark on the 100-mm line. The PhGADA ranged from 0-100.

A listing of all observed data based on the All Randomized Analysis Set will display the PhGADA at Screening, Day 1, and Week 13; and the percent change from baseline in PhGADA and associated arthritis responder/non-responder status at Week 13.

8. SAFETY ANALYSES

Safety analyses will be conducted on the Safety Analysis Set and Extension Phase Safety Analysis Set, defined in Section 3.1.3.

Safety data during the double-blind phase will be summarized based on actual treatment while the subject is on double-blind study drug. Subjects will be included in analysis after first dose date of double-blind study drug up to:

- First dose date of open-label filgotinib or first date in extension phase (minus 1 day for adverse events) for subjects who receive open label filgotinib or standard of care in extension phase
- Last dose date of double-blind study drug + 30 days (subjects meeting pre-specified sperm decrease thresholds at/prior to Week 13 who were switched to Monitoring Phase to assess reversibility of all sperm parameters meeting decrease thresholds; subjects permanently discontinued from study drug at/prior to Week 13)

Safety data during the extension phase will be summarized based on actual treatment sequence as described in Section 3.2 of this SAP. Safety data collected on (AEs only) or after first dose date of open-label filgotinib/first date in extension phase to:

- Last dose date of open-label filgotinib/standard of care in extension phase + 30 days will be included for subjects who have stopped or completed all study drug/SOC in the extension phase
- All available data (after start of extension phase) at time of data cut for subjects who are ongoing on open-label filgotinib/standard of care in the extension phase at the time of an interim analysis

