## **6.7. Early Termination**

Subjects who discontinue study participation for any reason prior to Week 156 in the Extension Phase, prior to reaching Reversibility or Week 52 in the Monitoring Phase (whichever occurs first) will complete an ET Visit. Subjects on blinded study drug or open-label filgotinib will also undergo a routine safety follow-up visit 30 days ( $\pm 5$  days) after the last dose of study drug.

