**Appendix 2. Study Procedures Table – Double-blind Treatment Phase (Section 6.4)**

EVENT	Screening						ET b	Safety follow-up c 30 Days after last dose of study drug (±5 days)
		Day 1	W2 (±5 days)	W4 (±5 days)	W8 (±5 days)	W13** (+5 days)		
Study days (D)/weeks (W) a								
Informed Consent	X							
Demographics and Medical History (Disease Characteristics, RA/PsA/AS/nrAxSpA History, Number of Children Fathered, Smoking Habits, Average Weekly Alcohol Consumption, and Family History of Coronary Heart Disease)	X							
Inclusion/exclusion criteria review	X	X						
Complete Physical Exam c	X						X	X
Symptom-directed Physical Exam, as needed		X	X	X	X	X		
Vital Signs c and Weight	X	X	X	X	X	X	X	X
Height	X							
12-lead ECG	X						X	X
Tender Joint Count 28 (TJC28) (for RA subjects only)	X							
Swollen Joint Count 28 (SJC28) (for RA subjects only)	X							
Tender Joint Count 68 (TJC68) (for PsA subjects only)	X							
Swollen Joint Count 66 (SJC66) (for PsA subjects only)	X							

EVENT	Screening						ET b	Safety follow-up c 30 Days after last dose of study drug (±5 days)
		Day 1	W2 (±5 days)	W4 (±5 days)	W8 (±5 days)	W13** (+5 days)		
Study days (D)/weeks (W) a								
Patient Global Assessment of Disease Activity (PtGADA) (for RA and PsA subjects only)	X							
Physician's Global Assessment of Disease Activity (PhGADA) d (for all subjects)	X	X					X	
Patient's Global Assessment of Pain Intensity (PPain) (for PsA subjects only)	X							
Bath Ankylosing Spondyloarthritis Disease Activity Index (BASDAI) (for AS/nrAXSpA subjects only)	X							
TB (Quantiferon ® ) Test e	X							
Chest X-ray f	X							
Urinalysis g	X	X					X	X
Urine drug screen g	X							
Hematology and Serum Chemistry g	X	X	X	X	X	X	X	X
Lipid profile (fasting) (Total cholesterol and subfractions) g		X					X	
Serum hsCRP	X	X	X	X	X	X		
Endocrine: TSH, HbA1c g	X							

EVENT	Screening						ET b	Safety follow-up c 30 Days after last dose of study drug (±5 days)
		Day 1	W2 (±5 days)	W4 (±5 days)	W8 (±5 days)	W13** (+5 days)		
Study days (D)/weeks (W) a								
LH, FSH, inhibin B, total Testosterone collection time between 07:00-11:00 in the morning g	X	X		X		X	X	X
PK collection (sparse) h			X	X		X		
Concomitant Medications	X	X	X	X	X	X	X	X

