FU-4*	Last Dose Date OL filgotinib (filgo to OL filgo); last dose date DB drug*, otherwise + 30 Days	Last Dose Date OL filgotinib (filgo to OL filgo); last dose date DB drug*, otherwise + 8 Days	Last Dose Date OL filgotinib (filgo to OL filgo); last dose date DB drug*, otherwise + 35 Days

Note: Data will be included for “on-treatment” visits up to the last dose date of standard of care in the extension phase (if non-missing) or up to last dose date of any study drug + 7 days.

*FU-4 visit collected based on days from last dose of open-label filgotinib (filgotinib 200 mg to OL filgotinib); EXT days for all (prior to Amendment 1) subjects / only non-responders (after Amendment 1) who switched to standard of care in extension phase; and from last dose date of double-blind study drug for those meeting sperm decrease threshold at Week 13 or prematurely discontinued in/at end of double-blind phase. Protocol specified an upper bound of + 5 days. FU-4 visit window is applicable for hematology, chemistry, vitals, and weight.

Table 3-3. Analysis Visit Windows for LH, FSH, Inhibin B, and Total Testosterone

Analysis Visit	Nominal Day (Study Day)	Lower Limit (Study Day)	Upper Limit (Study Day)
Baseline	1	None	1
Week 4	29	2	84
Week 13	92	85	112
Week 26	183	170	260
Week 39	274	261	351
Week 52	365	352	442
Week 65	456	443	533
Week 78	547	534	624
Week 91	638	625	715
Week 104	729	716	806
Week 117	820	807	897
Week 130	911	898	988
Week 143	1002	989	1079
Week 156	1093	1080	≥ 1093
FU-4*	Last Dose Date OL filgotinib (filgo to OL filgo); last dose date DB drug*, otherwise + 30 Days	Last Dose Date OL filgotinib (filgo to OL filgo); last dose date DB drug*, otherwise + 8 Days	Last Dose Date OL filgotinib (filgo to OL filgo); last dose date DB drug*, otherwise + 35 Days

Note: Data will be included for “on-treatment” visits up to the last dose date of standard of care in the extension phase (if non-missing) or up to last dose date of any study drug + 7 days.

*FU-4 visit collected based on days from last dose of open-label filgotinib (filgotinib 200 mg to OL filgotinib); off study drug but in EXT phase for all (prior to Amendment 1) subjects / only non-responders (after Amendment 1) who switched to standard of care in extension phase; and from last dose date of double-blind study drug for those meeting sperm decrease threshold at Week 13 or prematurely discontinued in/at end of double-blind phase. Protocol specified an upper bound of + 5 days.

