8.2.2.1. Treatment-Emergent Laboratory Abnormalities

Treatment-emergent laboratory abnormalities during the double-blind phase are defined as values that increase at least 1 toxicity grade from baseline at any postbaseline time point, up to the first dose date of open-label filgotinib/first date in extension phase (if non-missing) or to the date of last dose of double-blind study drug plus 30 days for subjects who permanently discontinued double-blind study drug (and did not continue to extension phase).

Treatment-emergent laboratory abnormalities during the extension phase are defined as values that increase at least 1 toxicity grade from baseline at any postbaseline time point after first dose date of open-label filgotinib/first date in extension phase to last dose date of open-label filgotinib/standard of care in extension plus 30 days or to the last available date in the database snapshot for subjects who were on extension phase treatment at the time of an interim analysis.

If the relevant baseline laboratory value is missing, any abnormality of at least Grade 1 observed within the time frame specified above will be considered treatment emergent.

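### For men who stop study drug, follow-up samples on days 31–35 are assigned to the FU-4 visit but fall outside the SAP's 30-day safety data rules

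*SAP*

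**What the plan says.** **Visit schedule.** Protocol 6.7 says that men leaving the study while on blinded drug or open-label filgotinib "will also undergo a routine safety follow-up visit 30 days" after the last dose, with a tolerance of 5 days either way. Protocol 6.8 and the procedures tables in Protocol Appendix 2 give the same timing. SAP Appendix 1 reproduces those tables, so the difference in protocol version between the two documents does not matter here.

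**Analysis window.** SAP Tables 3-1 and 3-2 place FU-4 from last dose + 8 to last dose + 35 days; the upper limit reads "last dose date DB drug*, otherwise + 35 Days". The footnotes give the reason: "Protocol specified an upper bound of + 5 days". Table 3-1 applies the window to urinalysis. For Table 3-2 the footnote states that the "FU-4 visit window is applicable for hematology, chemistry, vitals, and weight".

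**Data period.** For double-blind safety data, SAP Section 8 gives the limit "Last dose date of double-blind study drug + 30 days (subjects meeting pre-specified sperm decrease thresholds" and extends it to men permanently off drug by Week 13. For the extension it stops 30 days after the last open-label filgotinib dose, or 30 days after the end of Standard of Care. SAP 8.2.2.1 runs treatment-emergent laboratory abnormalities "to the date of last dose of double-blind study drug plus 30 days for subjects who permanently discontinued double-blind study drug"; this limit is confined to men who never entered the extension, and a matching one is set for open-label filgotinib. Neither section makes an exception for FU-4. Protocol 8.5.4 also uses 30 days for safety data, but leaves room for another period to be specified.

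**The concern.** The SAP widened the FU-4 window so that it would take in every compliant follow-up visit, then closed the safety data period five days short of it. For a man who leaves blinded drug because of a sperm decrease, who stops early, or who stops open-label filgotinib, this visit is the scheduled off-drug safety sample. Whether a new abnormality is counted would then depend on which compliant day he attended.

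No other summary picks up the sample. SAP 8.2 plans laboratory summaries for the double-blind and extension phases only; none is specified for the Monitoring Phase.

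**Working it through.** **1. The plan's own figure.** Nominal day 30 plus the protocol tolerance of 5 gives 30 + 5 = 35, which matches the FU-4 upper limit.

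**2. Days outside the data rule.** SAP 3.7.1 counts follow-up day as assessment date minus last dose date, so day 30 is the last day inside a + 30 cut-off.
- Compliant days: 25 to 35, which is 11 days.
- Compliant days past the cut-off: 31 to 35, which is 5 days.
- Share of compliant days: 5/11 = 45.5%.
- Share of the whole FU-4 window (days 8 to 35, 28 days): 5/28 = 17.9%.

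**3. From days to samples.** The documents do not say when visits occur within the window. Under assumed timing on days 25–35, the share of samples after day 30 would be:

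| Assumed timing | Share on days 31–35 |
|---|---|
| Even spread | 5/11 = 45.5% |
| Triangular, weights 6 − \|d − 30\| | 15/36 = 41.7% |
| Normal, centre 30, SD 1 / 2 / 3 | 31% / 40% / 43% |
| Normal, centre 28, SD 1 / 2 / 3 | 1% / 11% / 22% |
| Normal, centre 32, SD 1 / 2 / 3 | 93% / 76% / 65% |

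For the normal rows, day d has weight Φ((d + 0.5 − m)/s) − Φ((d − 0.5 − m)/s), and the share is the sum over days 31–35 divided by the sum over days 25–35. The range of 1% to 93% shows that the documents fix the share of days but not the share of samples.

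**4. Who is affected.** Under SAP 3.7.1, a man switched to Standard of Care starts the extension the day after his last blinded dose. Section 8 then keeps his data to the end of Standard of Care + 30 days, or to the data cut if he is ongoing. His follow-up sample on days 31–35 lies inside that period. If a fraction f of FU-4 visits comes from such men, the overall share under even spread is (1 − f) × 45.5%: 34% at f = 0.25, 23% at f = 0.50, 11% at f = 0.75. The documents give no value for f.

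**5. One case traced through.** Take a man with a sperm decrease whose last blinded dose is on Day 100. Blood is drawn on Day 133 (133 − 100 = 33, compliant) and shows a new Grade 3 neutrophil count.
- Table 3-2: assigned to FU-4.
- 8.2.2.1: not treatment-emergent, because 33 > 30. It drops out of the graded and Grade 3 or 4 tables.
- 8.2.2.2: marked abnormalities must arise during the phase, so day 33 does not qualify if the phase ends at + 30.
- 8.2.2.3: the focused listing covers treatment-emergent Grade 3 or 4 values, so this value alone would not bring him into it.
- 8.2.1 and 8.2.3: on the literal reading of Section 8, it is also missing from the FU-4 by-visit summary and, for liver tests, from the reporting-period liver table.
- 8.2: the general by-subject listing has no stated day limit, so the value appears there and is flagged.

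Drawn on Day 129 (129 − 100 = 29), the same value enters all of these outputs.

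**6. After the change.** With a + 35 cut-off, 0 of the 11 compliant days fall outside.

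**The case against.** The best defence has four parts.

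*The specific rule governs.* FU-4 is a purpose-built window, and a statistician could let it override the general paragraph in Section 8 for by-visit tables. That is a fair reading, so loss from the FU-4 by-visit summary is not certain. It does not rescue the abnormality tables, because 8.2.2.1 states its own + 30 limit.

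*Thirty days is the protocol's rule and matches the adverse-event definition.* True, and a common cut-off is defensible. But Protocol 8.5.4 allows another period, and the SAP had already recognised the extra 5 days when it set FU-4. As written, the two rules disagree.

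*Nothing disappears.* The general laboratory listing keeps and flags the values. Abnormalities that need intervention or cause symptoms are recorded as adverse events (Protocol 7.5), and the SAP lists all adverse events whether treatment-emergent or not. This largely stands. The loss is from summaries and from the treatment-emergent flag. The adverse-event route is narrower for men in the Monitoring Phase, where Protocol 7.3 asks for procedure-related and serious events.

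*No bias is shown.* In the double-blind phase the rule treats both arms alike, and that stands. A reader might infer that the rule hides filgotinib abnormalities relative to placebo; nothing in the documents supports this for the randomised comparison. Only the loss at the end of open-label treatment is specific to filgotinib, and it has no concurrent placebo group.

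**Conclusion.** The conflict is real and limited. It affects men who stop blinded drug without entering the extension (Week 13 sperm decliners and early stoppers) and men who stop open-label filgotinib. For them, samples on 5 of the 11 compliant days are assigned to FU-4, yet fall outside the safety data period and the treatment-emergent laboratory definition. Loss from the treatment-emergent tables and the Grade 3 or 4 listing follows directly from 8.2.2.1. Loss from the FU-4 by-visit and liver summaries rests on reading Section 8 literally.

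A reader might infer that nearly half of all follow-up samples are lost. The documents do not support that. The 45.5% is a share of calendar days and becomes a share of samples only if visits are evenly spread. Men continuing on Standard of Care are unaffected, and the numbers of men in the affected groups are not given. The primary and secondary semen endpoints are untouched.

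**What to change.** In SAP Section 8, for both reporting periods and for study-drug stoppers only, and in 8.2.2.1, extend the cut-off for laboratory, urinalysis, vital-sign and weight data from last dose + 30 to last dose + 35 days, the FU-4 upper limit. The liver table in 8.2.3 then follows. Keep the adverse-event definition at 30 days, as in Protocol 8.5.6. Document the change; SAP Section 1 sends changes after finalisation to the clinical study report.

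The cost is a few words and one date constant. There are two downsides:
- The laboratory period gains up to 5 off-drug days, which for men entering the Monitoring Phase may be days on newly started Standard of Care. No other scheduled Monitoring Phase visit enters, since the next is at about 13 weeks.
- The laboratory cut-off would be 5 days later than the adverse-event cut-off. An abnormality on days 31–35 could then be treatment-emergent as a laboratory value but not as an adverse event. A table footnote should say so.

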8.1. Adverse Events and Deaths

8.1.1. Adverse Event Dictionary

Clinical and laboratory adverse events (AEs) will be coded using the current version of MedDRA. System organ class (SOC), high-level group term (HLGT), high-level term (HLT), preferred term (PT), and lower-level term (LLT) will be provided in the AE dataset.

8.1.2. Adverse Event Severity

Adverse events are graded by the investigator as Grade 1, 2, 3, 4, or 5 according to Common Terminology Criteria for Adverse Events (CTCAE) Grading Scale. If CTCAE criteria do not exist for a specific event, Table 7-1 of the study protocol provides guidance for the investigator to grade the event. The severity grade of events for which the investigator did not record severity will be categorized as “missing” for tabular summaries and data listings. The missing category will be listed last in summary presentation.

8.1.3. Relationship of Adverse Events to Study Drug

Related AEs are those for which the investigator selected “Related” on the AE eCRF to the question of “Related to Study Treatment.” For the extension phase, AEs marked as “Related to SOC” will be considered as related for subjects who switch to SOC in the extension phase. Relatedness will always default to the investigator’s choice, not that of the medical monitor. Events for which the investigator did not record relationship to study drug will be considered related to study drug for summary purposes. However, by-subject data listings will show the relationship as missing.

8.1.4. Serious Adverse Events

Serious adverse events (SAEs) will be identified and captured as SAEs if the AEs met the definitions of SAEs that were specified in the study protocol. SAEs captured and stored in the clinical database will be reconciled with the SAE database from the Gilead Global Patient Safety (formerly Gilead Pharmacovigilance and Epidemiology) Department before database finalization.

8.1.5. Treatment-Emergent Adverse Events

8.1.5.1. Definition of Treatment-Emergent Adverse Events

Treatment-emergent adverse events (TEAEs) during the double-blind phase are defined as 1 or both of the following:

- Any AEs with an onset date on or after the double-blind study drug start date through first dose date of open-label filgotinib/start date in extension phase minus 1 day (if subject enrolled in extension phase) or to last dose date of double-blind study drug + 30 days for subjects who permanently discontinue double-blind drug and do not enroll into extension phase (including subjects who meet a sperm decrease threshold who stop study drug and continue to be followed in the monitoring phase for reversibility)
- Any AEs leading to premature discontinuation of double-blind study drug

Treatment-emergent adverse events (TEAEs) during the extension phase are defined as 1 or both of the following:

- Any AEs with an onset date on or after first dose date of open-label filgotinib/first dose date in extension phase to last dose date of open-label filgotinib + 30 days for subjects who permanently discontinue open-label filgotinib (including subjects who meet a sperm decrease threshold who stop study drug and continue to be followed in the monitoring phase for reversibility) or all AEs for subjects who are ongoing on open-label filgotinib/standard of care in extension phase at the time of an interim analysis
- Any AEs leading to premature discontinuation of open-label filgotinib study drug

For example, for a subject who took double-blind placebo and switched to standard of care in the extension phase, TEAEs with an onset date on/after first dose date of double-blind filgotinib and prior to first date in extension phase will be TE for double-blind filgotinib (summarized with double-blind phase); from first date in extension phase up to last dose date of standard of care in extension phase + 30 days will be TE for standard of care (summarized by treatment sequence [double-blind filgotinib to standard of care] for the extension phase).

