### **6.4. Double-blind Treatment Phase (Day 1 Through Week 13 Study Visit)**

All subjects will receive blinded study drug until completion of all Week 13 assessments.

Study assessments will be completed as specified in the Study Procedures Table ([Appendix 2](#)).

Invasive study procedures such as blood draws should be done at the end of a study visit, as much as possible.

The end of the Double-Blind Treatment Phase is when the Week 13 semen results are available to the investigator and have been evaluated. Based on this evaluation, subjects are assigned to enter the Monitoring Phase or the Extension Phase.

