**Figure 6-1. Semen Collection Schema**

A standardized procedure for semen collection and analysis will be provided to sites in a separate manual. Semen will be assessed locally for all parameters (motility, concentration, count, and volume), except morphology, which will be assessed centrally.

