3.7. Analysis Visit Windows

3.7.1. Definition of Study Day

The First Dosing Date of Double-Blind Filgotinib/Placebo is defined as the date when subjects take their first dose of double-blind filgotinib/placebo as recorded on the Study Drug Administration eCRF.

The Last Dosing Date of Double-Blind Filgotinib/Placebo is defined as the date when subjects take their last dose of double-blind filgotinib/placebo as recorded in the Study Drug Administration eCRF.

The Last Dosing Date of Any Filgotinib is defined as the date when a subject takes their last dose of double-blind or open-label filgotinib as recorded in the Study Drug Administration eCRF.

The Start Date of Extension Phase is defined as the first dose date of open-label filgotinib (for rheumatic disease responders randomized to filgotinib who continued on open-label filgotinib in extension phase) from the study drug administration eCRF or last dose date of double-blind study drug +1 day for subjects who have a non-missing standard of care start date in the extension phase of the study. In some countries, it takes time to obtain a new standard of care drug for rheumatic disease when subjects undergo a medication switch (especially for biologics), so the “standard of care” is to continue background medications alone or in rare cases, to take no rheumatic disease medication until the new regimen is available.

The End Date of Extension Phase is defined as last dose date of open-label filgotinib as recorded on the Study Drug Administration eCRF for subjects on open-label filgotinib in the Extension Phase. The end date for standard of care in extension phase will be 1 day prior to the date the subject went into the Monitoring Phase (ie, date the site was notified of subject meeting a prespecified sperm decrease threshold). Subjects who do not participate in Monitoring Phase but have a Study Completion eCRF that states that the subject has either completed study or prematurely discontinued study will have the last date of standard of care estimated using the last of the following dates: last Covance lab date, last eCRF visit date, date of last sperm sample collection, and death date (if subject died).

Study Day will be calculated from the first dosing date of double-blind filgotinib/placebo and derived as follows:

- For postdose study days: Assessment Date – On-Filgotinib/Placebo Study Day 1 + 1
- For days prior to the first dose: Assessment Date – On-Filgotinib/Placebo Study Day 1

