8.1.6. Summaries of Adverse Events and Deaths

A brief, high-level summary of the number and percentage of subjects who experienced at least 1 TEAE in the categories described below will be provided by treatment (by double-blind treatment for double-blind phase; by treatment sequence for extension phase):

- TEAE
- TEAEs with Grade 3 or higher (further broken down to Grade 3, Grade 4, and Grade 5)
- TEAEs with Grade 2 or higher
- TE treatment-related AE
- TE treatment-related AEs with Grade 3 or higher (further broken down to Grade 3, Grade 4, and Grade 5)
- TE treatment-related AEs with Grade 2 or higher
- TE SAE
- TE treatment-related SAE
- TEAE that led to premature discontinuation of double-blind study drug (NOTE: category applicable only for double-blind phase)

- TEAE that led to premature discontinuation of open-label filgotinib study drug (NOTE: category applicable only for extension phase)
- TEAE that led to temporary interruption of double-blind study drug (NOTE: category applicable only for double-blind phase)
- TEAE that led to temporary interruption of open-label filgotinib (NOTE: category applicable only for extension phase)
- TEAE that led to premature discontinuation of study
- All deaths observed in the study (if a subject received \geq 1 dose of open-label filgotinib or standard of care in extension phase, the death will be summarized in extension phase; if the last study drug received was double-blind drug, the death will be summarized with the double blind phase)

The number and percentage of subjects who experienced at least 1 TEAE will be provided and summarized by SOC, HLT, PT, and treatment (double-blind treatment for double-blind phase; treatment sequence for extension phase).

For other AEs described below, summaries will be provided by SOC, PT, and treatment (double-blind treatment for double-blind phase; treatment sequence for extension phase):

- All TEAEs
- All TEAEs by Concomitant Medication Use (Immunomodulator and Corticosteroid Use)
- TEAEs of Grade 3 or higher (by maximum severity)
- TEAEs of Grade 2 or higher
- All TE treatment-related AEs
- TE Treatment-related AEs of Grade 3 or higher (by maximum severity)
- TE SAEs
- TE SAEs by Concomitant Medication Use (Immunomodulator and Corticosteroid Use)
- TE treatment-related SAEs
- TEAEs leading to temporary interruption of double-blind study drug (NOTE: table applicable only for double-blind phase)

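### Among men entering the Extension Phase, the date that closes the double-blind safety window is derived differently by route, so any dose-free wait before open-label dosing lengthens the window for filgotinib responders only

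*SAP*

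**What the plan says.** SAP 8.1.5.1 closes the double-blind TEAE window for men who enrol in the Extension Phase "through first dose date of open-label filgotinib/start date in extension phase minus 1 day". Men who do not enrol, in either arm, are followed "or to last dose date of double-blind study drug + 30 days for subjects who permanently discontinue double-blind drug". SAP 8 (opening text) and SAP 8.2.2.1 use the same anchor date for safety data generally and for laboratory abnormalities, without the one-day subtraction for laboratory values.

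SAP 3.7.1 gives the anchor date two meanings. For responders randomised to filgotinib, "The Start Date of Extension Phase is defined as the first dose date of open-label filgotinib". For men moving to Standard of Care it is "last dose date of double-blind study drug +1 day for subjects who have a non-missing standard of care start date in the extension phase". Under Protocol 3.1, every placebo man entering the Extension goes to Standard of Care, as do filgotinib non-responders. Only filgotinib responders go to open-label drug.

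On dosing around Week 13, Protocol 6.4 says: "All subjects will receive blinded study drug until completion of all Week 13 assessments". The same section ends the double-blind phase only when the semen results have been received and evaluated. Semen is analysed locally, "except morphology, which will be assessed centrally" (Protocol 6.11, text with Figure 6-1).

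SAP 8.1.6 plans "A brief, high-level summary of the number and percentage of subjects who experienced at least 1 TEAE", and its tables are crude counts and percentages. Exposure-adjusted incidence rates (EAIRs) for the double-blind phase are planned only for adverse events of interest and SAEs (SAP 8.1.7).

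**The concern.** The double-blind phase is the trial's only randomised, blinded safety comparison, so its observation window should not depend on which arm a man was in. Here it can. Take two responders who stop blinded tablets on the same day and wait the same time for semen results. An adverse event during the wait is a double-blind event if the man was on filgotinib. It is an extension-phase event if he was on placebo and has a recorded Standard of Care start date. The same wait is therefore credited to the double-blind tables for one route and to the extension tables for the other. Among Extension entrants this rule can lengthen the filgotinib window but never shorten it, and the crude percentages contain no correction.

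**Working it through.** The documents give no figure for the window length or for the gap, so there is no planned number to reproduce.

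**1. Window end by route.** Let L be the last blinded dose date, O the first open-label dose date, and g = O − L − 1 the number of dose-free days between them. For adverse events:

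| Route | Anchor date | Window closes |
|---|---|---|
| Filgotinib responder to open-label | O | O − 1 = L + g |
| Filgotinib non-responder to Standard of Care | L + 1 | L |
| Placebo entrant to Standard of Care (start date recorded) | L + 1 | L |
| Not entering the Extension, either arm | none | L + 30 |

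Among entrants, the excess for filgotinib responders is exactly g days.

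**2. What the documents allow for g.** Protocol 6.4 keeps men on blinded drug through all Week 13 assessments, and the Definition of Terms counts the semen collection visits as part of Week 13. The 14-day two-sample period is therefore on drug. Only the time from the last sample to evaluated results and the open-label start can be dose-free, and no length is given for it.

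**3. Effect on crude percentages.** Assumptions: 91-day window, constant hazard, true TEAE incidence of 40% in both arms, and 60% of the filgotinib arm being responders who go to open-label drug.

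- h = −ln(1 − 0.40)/91 = 0.005614 per day
- Added points = 0.6 × [1 − exp(−h(91 + g)) − 0.40] × 100
- g = 0: 0
- g = 7: 0.6 × (42.3 − 40.0) = 1.4 points
- g = 14: 0.6 × (44.5 − 40.0) = 2.7 points

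A fuller version adds the non-entrants at 121 days in both arms. Let e be the share entering the Extension and r the responder share among filgotinib entrants. At a 40% TEAE rate, with e from 0.8 to 0.9 and r from 0.5 to 0.9, the added points are 0.9 to 1.9 at g = 7 and 1.8 to 3.7 at g = 14. At e = 0.8 and r = 0.7, TEAE rates of 20%, 40% and 60% give 0.8, 1.3 and 1.5 points for g = 7.

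**4. Net window difference when entry differs by arm.** Mean window on filgotinib = e_F(91 + r·g) + (1 − e_F)·121. Mean window on placebo = e_P·91 + (1 − e_P)·121. With r = 0.7:

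- e_F = 0.9, e_P = 0.8: (94.0 + 0.63g) − 97.0, which is −3.0 days at g = 0, +1.4 at g = 7 and +5.8 at g = 14
- e_F = 0.8, e_P = 0.9: (97.0 + 0.56g) − 94.0, which is +3.0, +6.9 and +10.8 days

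The 30-day rule for non-entrants can therefore offset, reverse or add to the effect of g.

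**5. Exposure-adjusted rates.** SAP 8.1.5.3 ends double-blind person-time at the earliest of last blinded dose + 30 days, extension start − 1 day, death, or data cutoff. This follows the event window except for a gap beyond 30 days, where person-time is capped but the TEAE definition for entrants is not.

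**The case against.** The strongest reply is that there may be no gap at all. Protocol 3.1 assigns men as soon as results are evaluated. It describes non-responders and men meeting a sperm threshold as stopping blinded drug at that point, and filgotinib responders as converting to open-label drug. Protocol 3.3 describes men as on double-blind treatment when they enter Monitoring. No blinded drug is dispensed at Week 13 (Appendix 2, footnote o). However, bottles hold 30 tablets (Protocol 5.2.2) and Weeks 8 to 13 are 35 days. If two bottles were given at Week 8, 60 − 35 = 25 tablets would remain. This stands: g = 0 is compatible with the protocol, and so is g > 0.

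A reader might go on to infer four stronger things, which the documents do not support:

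- **That filgotinib percentages are inflated.** This needs g > 0, and step 4 shows that the net window can favour either arm.
- **That the gap could reach about 28 days, giving 4 to 5 points.** That requires counting the semen collection period as dose-free, which Protocol 6.4 and the Definition of Terms contradict.
- **That the EAIRs carry the same bias.** Events and person-time share nearly the same cut, and non-entrants in both arms contribute off-drug days. These rates cover SAEs and all events in the infections class.
- **That every placebo man is cut at his last dose.** Non-entrants get 30 more days, and the last-dose rule needs a recorded Standard of Care start date.

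It is also fair that SAP 3.7.1 gives a practical reason for its rule, namely delays in obtaining a new drug. The by-subject AE listing would also let a reader find the events in the wait. Neither point corrects the summary tables.

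**Conclusion.** The arm-dependent rule is in the text and follows directly from reading SAP 8, 8.1.5.1 and 8.2.2.1 with 3.7.1. Its effect is conditional and probably modest. It is nil if blinded dosing runs until the results are evaluated. Under the stated assumptions of a 40% TEAE rate, 60% affected and constant hazard, it is about 1.4 percentage points on the filgotinib arm for a 7-day turnaround and about 2.7 for 14 days. It touches filgotinib responders only and matters for the crude adverse-event and laboratory-abnormality tables, not materially for the EAIRs. The direction of the net arm difference cannot be settled without the Extension entry rates and the actual gap. The change is still worth making, because it removes the dependence on arm for any gap and alters nothing if there was none.

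**What to change.** For every Extension entrant in either arm, end the double-blind safety window at the last double-blind dose and start the extension safety window the next day, whichever treatment follows. Apply this in SAP 8, 8.1.5.1, 8.1.5.3 and 8.2.2.1, and carry it into the partial-date rules of 8.1.5.2. Define it as a safety-specific date and leave the 3.7.1 definition alone, since the note to Table 3-4 also uses the extension start to select semen data. The rule then also covers entrants without a recorded Standard of Care start date, for whom 3.7.1 gives no start. Report the distribution of days between last blinded and first open-label dose. SAP 1 allows changes after finalisation to be documented in the CSR.

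The cost is one date derivation. A few events that began before the first open-label dose will move into the filgotinib-to-open-label extension table, which should be footnoted. The 30-day window for non-entrants is unchanged, so any imbalance from differing entry rates remains (−3.0 or +3.0 days in the two examples in step 4). If the main rule is kept, the minimum is to report the gap and repeat the crude tables with the cut at the last blinded dose.
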